7.2.1 Baseline Behavioral Questionnaire

A staff member will access the Web page for the questionnaire and enter a password to log in. Next, the staff member will enter the participant's ID and date and let the participant complete the rest of the questionnaire. Initially, the participant will be presented simple practice questions (e.g., "choose all that applies," "indicate how many times," "choose one of a fixed set of answers"). Once the practice has been successfully completed, the participant will read a statement encouraging her to respond to all questions as truthfully as possible. Next, she will proceed to the Baseline Behavioral Questionnaire. This questionnaire will assess different types of sexual behavior (vaginal/anal/oral), condom use per act (with/without), partner gender (male/female), partner type (significant other/casual partner), and partner HIV status (positive, negative, unknown) in the recent past. It will also include questions on past use of vaginal hygiene products, medications, desiccants, douches, tampons, and vaginal pregnancy prevention methods. Participants will also be asked to report on substance use, and likelihood of using a microbicide in the future.

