7.2.2 Acceptability and Adherence Questionnaire

At the Two-Week Clinic Visit, the participant will once again fill in a Web-based survey. This time it will be the Acceptability and Adherence Questionnaire that will explore the experiences the participant had during the prior 14 days using the gel vaginally, her likes and dislikes concerning the gel, the applicator, the application process, any changes she may have introduced or may wish to introduce in the volume used, any problems (e.g. leakage) she may have had, partner's reaction, sexual enjoyment, condom use during sexual intercourse using the gel, changes in her habitual sexual behavior, and likelihood of using a microbicide in the future. This last section will have items worded very similar to those of the same section applied at baseline, so that

comparisons can be made regarding the anticipated likelihood of future microbicide use before and after becoming familiarized with the product.

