10.2.2 Secondary Endpoints

Consistent with the secondary study objectives to assess adherence to, and acceptability of, a short-term regimen of VivaGel[®], and to assess the effect of this regimen on vaginal microflora, the following endpoints will be assessed:

- The proportion of participants who report via adherence questionnaire that they were adherent to the product use regimen, with adherence defined as the application of at least 80% of the expected number of doses of study product over the two weeks of product use;

- The proportion of participants who at their Two-Week Clinic Visit report via the acceptability questionnaire that they would be very likely to use the candidate microbicide during sexual intercourse in the future;
- Reported positive and negative aspects of using study product;
- Changes in vaginal flora.

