10.10.2 Data Analysis

For analyses comparing VivaGel[®] to the VivaGel[®] placebo, data from approximately 43 women will be included (18 participants in each of the 2 arms plus 7 previously enrolled) whereas for analyses comparing VivaGel[®] to the HEC gel, data from approximately 36 women will be included (18 participants per arm). All references to “control gel” below apply to 1) the VivaGel[®] placebo in analyses comparing VivaGel[®] to the VivaGel[®] placebo and, 2) the HEC gel in analyses comparing VivaGel[®] to the HEC gel.

When the use of descriptive statistics to assess group characteristics or differences is required, the following methods will be used: for categorical variables, the number and percent in each category; for continuous variables, the mean, median, standard deviation, quartiles and range (minimum, maximum). Within-treatment group assessment of the change from the baseline measurement to a follow-up measurement will be analyzed using McNemar’s test (for categorical response variables) or the paired t-test or Wilcoxon signed-ranks test (for continuous variables). When use of formal testing to assess differences between users of the control gel and users of VivaGel[®] is required, the following methods will be used: for binomial response variables, chi-square tests and logistic regression; for continuous variables, t-tests and linear regression or nonparametric methods if data are non-Normal.

To assess the adequacy of the randomization, control gel and VivaGel[®] participants will be compared for baseline characteristics including demographics, pelvic examination, and laboratory measurements using descriptive statistics. Due to the small sample size, formal comparisons will not be done.

Primary Analyses

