An additional secondary study objective is to evaluate aspects of product acceptability. To evaluate acceptability, the proportion of participants who at their Two-Week Follow-up Visits report via acceptability questionnaire that they would be extremely likely to use the candidate microbicide during sexual intercourse in the future will be calculated by treatment arm. In addition, positive and negative aspects of using the study drug will be listed in order of frequency. All enrolled women with a Two-Week follow-up visit will be included in these analyses.

The final secondary study objective is to assess the effect of a twice-daily short-term regimen of VivaGel[®] on the vaginal microflora of sexually active HIV-uninfected women. To assess the effect of SPL7013 on vaginal flora, clinically significant changes in vaginal flora will be evaluated by the Nugent score with shift tables from baseline (Enrollment) to follow-up visits. The Nugent score is graded 1 to 10 as follows:

1. Normal, 0 to 3
2. Intermediate, 4 to 6

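### Willingness to use a microbicide is asked before and after gel use so the answers can be compared, but the acceptability analysis never makes that comparison

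*Supplement*

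**What the plan says.** **Collection.** Section 7.2.1 describes the Enrollment questionnaire: "Participants will also be asked to report on substance use, and likelihood of using a microbicide in the future". Section 7.2.2 repeats the topic at the Two-Week Clinic Visit in similar wording, so that "comparisons can be made regarding the anticipated likelihood of future microbicide use before and after becoming familiarized with the product".

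**Endpoint.** Section 10.2.2 (also Section 4.2 and the Schema) defines acceptability as the proportion of women who report at Two Weeks that "they would be very likely to use the candidate microbicide during sexual intercourse in the future". Reported likes and dislikes are a further endpoint.

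**Analysis.** Section 10.10.2, Secondary Analyses, gives the Two-Week proportion of women reporting that "they would be extremely likely to use the candidate microbicide during sexual intercourse in the future will be calculated by treatment arm". It adds that "positive and negative aspects of using the study drug will be listed in order of frequency". The Enrollment answer is not mentioned.

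**General methods.** Earlier in Section 10.10.2 there is a menu of methods. "Within-treatment group assessment of the change from the baseline measurement to a follow-up measurement will be analyzed using" McNemar's test, the paired t-test or the Wilcoxon signed-ranks test. Where formal testing between arms is required, the menu offers, "for binomial response variables, chi-square tests and logistic regression". Neither entry is assigned to the likelihood-of-use item. The baseline balance check names demographics, pelvic examination and laboratory measurements as examples, but not attitude to microbicides.

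**The concern.** The protocol collects paired answers for a stated purpose, and the analysis section does not carry that purpose through. Elsewhere Section 10.10.2 names the baseline when it means to use it: laboratory change is Two-Week minus baseline, and Nugent scores get shift tables from Enrollment. Acceptability gets neither.

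The secondary objective is to evaluate product acceptability. Women who join a microbicide trial may already favour microbicides. A Two-Week proportion in one arm therefore cannot show whether using the gel raised willingness, lowered it or left it unchanged. Following the plan as written leaves the question in Section 7.2.2 unanswered, although the data to answer it are already in hand.

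**Working it through.** **The plan's own figures.** The protocol gives no sizing for acceptability. Its only calculations are Tables 17 and 18, for safety events, and these reproduce. For example, at n = 18 and a true rate of 5%, P(0 events) = 0.95^18 = 0.397 and P(≥1) = 0.603, against the stated 0.40 and 0.60.

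**Inputs from the protocol.** There are 18 women per arm for VivaGel against HEC gel, and about 43 in total (taken as 21 and 22) for VivaGel against its placebo (Sections 10.4, 10.10.2). Allocation is randomised and stratified by site (10.5), and participants and staff are blinded (10.7).

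**Assumptions, because the protocol gives none.** Baseline top-category rate 30–70%; correlation ρ between the two answers 0.3–0.7; a five-category scale.

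**1. Within an arm.** Suppose 12 of 18 women (67%) are in the top category at Two Weeks.

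| Enrollment | Two Weeks | Change |
|---|---|---|
| 6/18 (33%) | 12/18 | +33 points |
| 12/18 (67%) | 12/18 | 0 |
| 15/18 (83%) | 12/18 | −17 points |

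The planned output is the same in all three rows.

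**2. Between arms: bias.** In simulations with no gel effect, 18 per arm and a 50% top-category rate, the mean difference between arms was within 0.001 of zero at ρ = 0.3, 0.5 and 0.7. Rejection by the uncorrected chi-square test was 6.6–6.7% throughout. That slight excess over 5% is small-sample behaviour of the test. It does not change with ρ, so prior attitude adds no bias.

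**3. Between arms: chance imbalance.** The SD of the baseline difference is √[p(1−p)(1/n₁ + 1/n₂)].

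| n per arm | p | SD (points) | P(gap ≥ 20 points) |
|---|---|---|---|
| 18, 18 | 0.3 or 0.7 | 15.3 | 0.20 |
| 18, 18 | 0.5 | 16.7 | 0.24 |
| 21, 22 | 0.3 or 0.7 | 14.0 | 0.16 |
| 21, 22 | 0.5 | 15.3 | 0.22 |

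**4. Precision.** On a continuous scale, baseline adjustment multiplies the standard error of the arm difference by √(1−ρ²): 0.95, 0.87 and 0.71 at ρ = 0.3, 0.5 and 0.7.

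**5. Where the power gain comes from.** The simulation used bivariate normal latent scores, five categories, a control top-category rate of 40% with the other four categories equal, and a 0.9 SD fall on VivaGel (top-category rate 12%). ρ was 0.5, with 18 per arm.

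| Analysis of the Two-Week answer | Power |
|---|---|
| Chi-square on top category | about 47% |
| Full scale, no baseline | about 68% |
| Full scale, adjusted for Enrollment | about 76% |

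The total gain is 76 − 47 = 29 points. Of this, 68 − 47 = 21 come from keeping the full scale and 76 − 68 = 8 from the baseline. Read these to within a few points.

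**6. Limits of a within-arm test.** An exact McNemar test needs at least six discordant pairs, all in one direction, for two-sided p < 0.05: 2 × 0.5⁶ = 0.031, whereas five pairs give 0.0625. With about 18 women, a shift table is more informative than the p-value.

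**The case against.** A reader might infer that prior attitude confounds the comparison of VivaGel with the control gels. The documents do not support that. The 54 later women are randomised 1:1:1 and the first seven were randomised 1:1 (Sections 4.5, 10.5), so allocation is balanced in expectation within each planned comparison. Participants are blinded. The chance gaps in step 3 are ordinary sampling variation.

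A reader might also credit the whole 29-point power gain to the Enrollment answer, or treat 47% as the power of a planned test. Neither holds. Most of the gain comes from abandoning the top-category cut. Section 10.10.2 only says the proportion will be calculated by arm; it commits to no acceptability test, whereas it says outright that Nugent distributions will be formally tested.

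Three further points have force.

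- The general menu in Section 10.10.2 already contains suitable within-arm methods, and the listing of likes and dislikes bears on acceptability. But the menu is not tied to this item, and a listing does not measure change.
- A Two-Week measure is a legitimate endpoint, since a woman cannot rate a gel she has not used. That is a reason to keep the proportion, not to leave the Enrollment answer unused.
- The Enrollment item concerns "likelihood of using a microbicide in the future", a general attitude, while the endpoint concerns the candidate gel during intercourse. The questionnaires are not in the documents, so the match between items is not established. This caveat stands.

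**Conclusion.** The point holds in a limited form. The before-and-after comparison announced in Section 7.2.2 is missing from the acceptability endpoint and its analysis. As planned, the within-arm result cannot separate prior attitude from experience with the gel. Between arms the cost is chance imbalance and lost precision, not bias.

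The imbalance figures rest only on an assumed baseline rate. The power figures also rest on an assumed 0.9 SD effect, ρ = 0.5 and a five-category scale, and should be read as illustration. This is a nearly free improvement to a secondary, descriptive analysis in a Phase 1 safety trial, and no safety conclusion depends on it.

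**What to change.** In Section 10.10.2, Secondary Analyses:

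1. Report the Enrollment likelihood-of-use answer by arm.
2. Report within-arm change from Enrollment to Two Weeks as a shift table, with McNemar's or the Wilcoxon signed-ranks test, both already on the protocol's menu.
3. As a supportive analysis, compare VivaGel with each control gel on the full Two-Week response scale, adjusted for the corresponding Enrollment item (linear or ordinal regression), with a 95% confidence interval.
4. Keep the top-category proportion as the stated descriptive endpoint.

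Two things come first. Reconcile the cut-point, since Section 10.2.2 says *very likely* and Section 10.10.2 says *extremely likely*. Confirm from the questionnaires which Enrollment item corresponds to the Two-Week item; if the wording differs materially, report the change as change in general willingness rather than in acceptability of this gel.

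The cost is analysis wording only: both questionnaires are already scheduled, and no visit, item or participant is added.

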3. BV, 7-10

Any shift from normal at baseline to intermediate or BV at a follow-up visit, or intermediate at baseline to BV at a follow-up visit, will be considered a clinically meaningful change in vaginal flora. Changes within each treatment arm will be reported. In addition, differences between the treatment groups in the distribution of Nugent scores at follow-up visits will be formally tested.

In addition to looking at shifts in the Nugent score, within treatment arm descriptions, and between treatment arm comparisons, will be done to assess clinically meaningful changes in quantitative measures of vaginal flora (defined by more than ≥ 1 log change in dominant members of the microflora, including *Lactobacillus* (H_2O_2 positive and negative strains), anaerobic gram negative rods, *Gardnerella vaginalis*, *Escherichia coli*, *Staphylococcus aureus*, *Candida* species, Group B *Streptococcus*, and *Enterococcus* species) and to assess differences in the quantitative levels of these flora between treatment arms during follow-up.

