- Sexually transmitted infection (STI) or reproductive tract infection (RTI) according to the 2006 Center for Disease Control (CDC) guidelines via lab tests at screening, or examination at screening or enrollment, and requiring treatment, including symptomatic bacterial vaginosis (BV) (clinical criteria or Gram stain evidence plus symptomatic discharge, odor, or itching), symptomatic candidiasis, other vaginitis, trichomoniasis, Chlamydia, gonorrhea, syphilis, active HSV lesions (HSV-2 seropositive not excluded except with active lesions), chancroid, pelvic inflammatory disease (PID), genital sores or ulcers, cervicitis, genital warts of the labia minora, vagina, or cervix, or any other symptomatic genital warts. *Note: Signs of asymptomatic BV may include the presence of white to grey homogeneous discharge, positive whiff test (amine odor) with addition of potassium hydroxide (KOH), pH greater than 4.5, presence of clue cells, a decrease in lactobacilli morphotypes, and increase in non-lactobacilli morphotypes. Women with clinical criteria or evidence of BV and with symptoms (symptomatic discharge, odor, itching) will be excluded. Women without symptoms, but with clinical or laboratory evidence of BV, are still eligible.*
- In the six months prior to enrollment, diagnosed with or treated for any STI (except genital HSV recurrence) or pelvic inflammatory disease
- Use of oral and/or vaginal preparations of antibiotic or antifungal medications, at Screening or within 30 days prior to the enrollment visit
- Participation in any other drug or device study within 30 days prior to enrollment visit
- Injected non-therapeutic drugs in the 12 calendar months prior to enrollment

- At screening or enrollment, any social or medical condition that, in the investigator's opinion, would preclude informed consent, make study participation unsafe, complicate interpretation of study outcome data, or otherwise interfere with achieving the study objectives.

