The primary aim of the study is to assess the toxicity of VivaGel[®] on vulvar and cervicovaginal mucosa. All visits in which a woman has been exposed to the study product will be included in the primary analysis of safety. Secondary intent to treat analyses may also be performed. To assess safety, the number and the percentages of participants experiencing at least one AE, and the number and percentage experiencing each specific AE will be tabulated by study arm. Each participant will contribute once in each category (i.e. only for highest severity AE for each participant) for the calculation of event rates. The number and percentage of participants experiencing each type of AE (including AEs leading to study discontinuation) will be tabulated by severity and relationship to treatment for each treatment group. AEs that lead to study product discontinuation will be listed in a separate data listing. Overall summaries by treatment group include the number and percentage of participants experiencing: (1) any experience; (2) any moderate, severe, or life-threatening experience. The number and percentage of participants with an AE judged possibly, probably or definitely related to study treatment will be summarized for each treatment group. Grade 3 or higher toxicity for hematology, coagulation function, liver function, or creatinine level is also a primary endpoint. Baseline and Two-Week visit laboratory measures will be summarized and the change in function, defined by the difference between Two-Week and baseline measurements, will be evaluated by treatment group.

Secondary Analyses

One secondary study objective is to assess adherence to a short-term regimen of VivaGel[®]. To assess adherence, the proportion of participants who applied 80% of the expected number of doses of study product over the two weeks of product use will be calculated by treatment arm. All enrolled women will be included in this analysis.

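### The between-arm tests of Nugent score and of culture levels are specified on follow-up values alone, although both are measured on every woman at Enrollment

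*Supplement*

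**What the plan says.** The relevant text is in the protocol, Version 3.0, Section 10.10.2 (Data Analysis). Letter of Amendment #1 does not change it.

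**Comparisons written on follow-up values only**
- Nugent score: "differences between the treatment groups in the distribution of Nugent scores at follow-up visits will be formally tested".
- Cultures: between-arm comparisons are planned "to assess differences in the quantitative levels of these flora between treatment arms during follow-up".

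**Analyses that do use baseline**
- Flora change is "evaluated by the Nugent score with shift tables from baseline (Enrollment) to follow-up visits". The meaningful change is defined as "Any shift from normal at baseline to intermediate or BV at a follow-up visit, or intermediate at baseline to BV at a follow-up visit". For these shifts the plan promises a report within each arm.
- A second culture endpoint is a "1 log change in dominant members of the microflora", described within arms and compared between arms.
- For laboratory values, "the change in function, defined by the difference between Two-Week and baseline measurements, will be evaluated by treatment group".

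**General methods.** The between-arm methods are, "for continuous variables, t-tests and linear regression or nonparametric methods if data are non-Normal", and chi-square tests and logistic regression for binary ones. No covariates are listed. Baseline characteristics are compared descriptively only.

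**Entry and data collection.** Section 5.3 states: "Women without symptoms, but with clinical or laboratory evidence of BV, are still eligible". Table 13 (Enrollment Visit) and Appendix I schedule Gram-stained smears and quantitative vaginal cultures for all women at Enrollment. Randomization is stratified by site only (Section 10.5).

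**The concern.** The effect on microflora is a named secondary objective (Section 3.2). For Nugent, the part of the plan that links baseline to follow-up is reported within arms, while the formal between-arm test compares follow-up distributions with no baseline term. The comparison of culture levels has the same form.

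A woman's flora at entry probably predicts her flora one to three weeks later. Leaving baseline out then has two costs. The comparison is noisier than it need be. And if one arm happens to start with more women with disturbed flora, part of that difference stays in the estimated gel effect, where it could resemble an effect or mask one. The plan would show such an imbalance descriptively but has no step that acts on it.

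A smaller, separate matter is the shift definition. It covers moves from normal or intermediate to a worse category. A woman with Nugent 7-10 at entry is eligible but cannot meet it. No denominator is stated, so a rate quoted over all women would be lower than the rate among those who can shift.

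**Working it through.** **The plan's own figures.** The only numerical design figures are the event probabilities in Tables 17 and 18 (Section 10.4). They reproduce: at a 5% true rate, the probabilities of at least 1 and at least 2 events are 0.603 and 0.226 for n=18 (stated 0.60 and 0.23), and 0.659 and 0.283 for n=21 (stated 0.66 and 0.28). There is no SD, effect size, alpha, power, correlation or BV prevalence for the flora comparisons, so the sizes below rest on stated assumptions.

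**Inputs from the documents.** VivaGel versus HEC gel: 18 per arm. VivaGel versus VivaGel placebo: about 43 women, taken as 21 and 22.

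**Step 1: precision.** For a continuous measure with equal variance at both times and correlation rho, the between-arm variance relative to a follow-up-only comparison is 1 - rho². The equivalent unadjusted size for arms of 18 is 18/(1 - rho²). The detectable difference at 80% power, two-sided 0.05 (assumed), is (1.96 + 0.84) × sqrt(1/n1 + 1/n2) × sqrt(1 - rho²), in SD units.

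| rho (assumed) | Variance factor | Equivalent n per arm | Detectable, 18 v 18 | Detectable, 21 v 22 |
|---|---|---|---|---|
| no adjustment | 1.00 | 18 | 0.93 | 0.85 |
| 0.3 | 0.91 | 19.8 | 0.89 | 0.82 |
| 0.5 | 0.75 | 24.0 | 0.81 | 0.74 |
| 0.7 | 0.51 | 35.3 | 0.67 | 0.61 |

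For an assumed true difference of 0.8 SD and 18 per arm, power is 0.67 on follow-up alone and 0.71, 0.79 and 0.92 with adjustment at the three correlations. For 21 versus 22 it is 0.75, rising to 0.79, 0.86 and 0.96.

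**Step 2: chance imbalance.** With 18 per arm, the difference in baseline means has standard error sqrt(2/18) = 0.33 SD. An imbalance of that size carries rho × 0.33 into a follow-up-only estimate: 0.10, 0.17 or 0.23 SD at rho 0.3, 0.5 or 0.7. In counts, if a share p of women enter with abnormal flora (assumed), and X1 and X2 are independent Binomial(18, p), then P(|X1 - X2| ≥ 3) is 0.29, 0.36 and 0.40 at p = 20%, 30% and 40%.

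**Step 3: the shift denominator.** If a share b of women have BV at entry and stay in the denominator, the reported rate is (1 - b) times the rate among women who can shift. With b = 25% and a 40% rate (both assumed), 0.75 × 0.40 = 30%. For an illustrative 40% versus 10% among women who can shift, with 18 per arm:

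| b (assumed) | Difference, all women | Power, all women | Power, women who can shift |
|---|---|---|---|
| 0% | 30 points | 0.55 | 0.55 |
| 10% | 27 | 0.49 | 0.51 |
| 20% | 24 | 0.43 | 0.46 |
| 30% | 21 | 0.38 | 0.41 |
| 40% | 18 | 0.32 | 0.36 |

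The relative risk stays at 4.0 throughout. Restricting the denominator therefore corrects the reported rate and difference but adds only about 1 to 4 points of power.

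**The case against.** **Much of the plan already uses baseline.** A reader might infer from the two follow-up-only comparisons that the flora and laboratory analyses as a whole ignore it. The text does not support that. Shift tables run from Enrollment, the 1-log culture endpoint is a change compared between arms, within-arm change is tested by paired methods, and laboratory values are analysed as Two-Week minus baseline. For the laboratory values, a baseline-adjusted model would be only an efficiency preference (variance factor 2(1 - rho) against 1 - rho²: 1.0 against 0.75 at rho 0.5, and 0.60 against 0.51 at rho 0.7).

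**Women with BV at entry can still contribute to the formal test.** It is tempting to say that they cannot worsen there. In a comparison of score distributions, a score of 7 to 9 can rise and a woman with BV can improve. The limitation belongs to the categorical shift definition alone, and even there a shift table gives these women their own row and the plan states no pooled rate.

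**Covariate lists are usually left to an analysis plan.** No separate analysis plan is shown, and linear and logistic regression are already allowed. This has force as regards detail. But the protocol does name what the formal Nugent test compares, and a more precise comparison is available from data already scheduled.

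**Chance imbalance does not invalidate a randomized test.** This is correct: the error rate allows for it. The loss is in precision and in how far the single observed estimate can be trusted, not in validity.

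**The sizes are assumed.** This also stands. The 1 - rho² gain applies to a continuous measure in a linear model and does not carry over directly to Nugent categories or to organisms that are often absent. Excluding symptomatic BV and recent antibiotic use may also narrow baseline flora.

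**Conclusion.** The point holds for two comparisons: the formal between-arm Nugent test and the between-arm comparison of culture levels. Both are specified without the baseline value that the schedule collects on every woman. With 18 to 22 women per arm the avoidable loss ranges from slight (9% of variance at rho 0.3) to large (49% at rho 0.7), and the documents do not show where in that range the trial lies.

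The shift denominator is a minor clarification. It is also separate from the main point: adjusting for baseline does not change which women a shift rate is counted over.

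This is a secondary objective in a small Phase 1 study with no power target for flora. The primary safety analyses are not affected, and nothing here makes the planned tests invalid. The change is worth making because it costs almost nothing.

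**What to change.** Amend the flora paragraphs of Section 10.10.2, or settle these points in an analysis plan before unblinding:

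1. **Nugent score.** Condition the between-arm test on baseline Nugent: a proportional-odds or linear model for the score with baseline as covariate, or a test stratified by baseline category.
2. **Culture levels.** Compare log10 levels between arms adjusted for the baseline level. For organisms that are often absent, use a rank-based or detected/not-detected analysis.
3. **Shifts (minor).** Report the proportion with a clinically meaningful worsening shift among women with baseline Nugent 6 or lower, and list women with BV at entry separately.

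The laboratory analysis can stay as it is. The cost is wording and programming only: no added visit, specimen or participant.
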